3.2 Measures Taken to Avoid and Minimize Bias

Multiple measures will be taken to avoid bias in this clinical study. First, the Advisor HD Grid Observational Study is prospective, such that the outcome of the study is unknown at time of enrollment, and all subjects must meet pre-defined eligibility criteria thereby minimizing selection bias. Next, guidance will be provided to sites regarding data collection for questionnaires and post-procedure follow-up visits and/or phone calls, and case report forms for data collection will be provided to all sites thereby minimizing inter-observer variability. Evaluation of arrhythmia recurrence via Holter monitoring will be performed by an independent core laboratory. Adverse events will be internally assessed by the Sponsor independent of assessment by the physician as reported by the site. Additionally, protocols are in place to minimize subjects lost to follow-up and collection of missing data to minimize the impact or bias caused by missing data.

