4.1 Descriptive Endpoint(s)

4.1.1 Outcomes Objective

The first objective is to quantify and characterize the acute- and long-term success rate of RF ablation after electroanatomical mapping with HD Grid and EnSite Precision with HD Wave in subjects with PersAF or VT.

Clinical Investigation Plan

To quantify and characterize the acute- and long-term success rate of RF ablation after electroanatomical mapping with HD Grid, the following will be summarized:

- Rate of acute success defined as the proportion of subjects who receive HD Grid mapping and RF energy delivery resulting in acute termination of clinical arrhythmia, defined by termination to SR (or AT if being treated for PersAF) or non-inducibility of clinical arrhythmia after ablation (cardioversion allowed prior to inducibility attempt).
- Rate of long-term success defined as the proportion of subjects who receive HD Grid mapping and RF energy delivery with the following pre-defined procedural endpoints:
 - Persistent AF (utilizing a 90-day blanking period following index ablation):
 - freedom from all atrial arrhythmias (AF/AFL/AT) greater than 30 seconds (as documented by 48-hr Holter at 12-month follow-up) and new or increased dose of class I/III antiarrhythmic drug (AAD).
 - freedom from all atrial arrhythmias (AF/AFL/AT) greater than 30 seconds (as documented by 48-hr Holter at 12-month follow-up) on or off class I/III AAD.
 - VT (utilizing a 14-day blanking period following index procedure):
 - freedom from recurrence of sustained monomorphic VT and new or increased dose of class I/III AAD at 6-month follow-up
 - freedom from recurrence of sustained monomorphic VT on or off class I/III AAD at 6-month follow-up.

Where recurrence of sustained monomorphic VT is defined as:

- Sustained monomorphic VT greater than 30s or requiring appropriate ICD pacing or shocks for patient with ICDs
- Sustained monomorphic VT greater than 30s recorded in follow-up visits or requiring intervention due to hemodynamic instability for patients without ICDs

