4.1.3 Additional descriptive endpoints

Additional descriptive endpoints include:

- Change in quality of life (QOL) at 6 and 12 months after receiving HD Grid mapping and RF ablation relative to baseline: defined as change in quality of life assessed in validated QOL surveys (EQ-5D and AFEQT for subjects with PersAF, EQ-5D and HADS for subjects with VT)
- Rate of periprocedural and immediate post procedural (48hrs) procedure- or device- related adverse events in all subjects in whom the HD Grid is inserted (regardless of RF energy delivery).
- Rate of procedure- or device-related adverse events and cardiovascular serious adverse events in all subjects in whom the HD Grid is inserted (regardless of RF energy delivery) through 30 days post study procedure.
- Proportion of VT subjects who receive HD Grid mapping and RF energy delivery free from recurrence of sustained monomorphic VT and new or increased dose of class I/III AAD, and free from recurrence of sustained monomorphic VT on or off class I/III AADs at 12-month follow-up outside the blanking period.
- Rate of repeat ablations after study procedure during 12-month follow up defined as proportion of subjects without an additional ablation procedure to treat indicated cardiac arrhythmia (outside blanking period, if applicable).
- For subjects treated for PersAF:
 - Proportion with atypical atrial flutter (AFL) identified during procedure
 - Of those receiving HD Grid mapping and RF ablation for AFL: Utility of HD Grid specific to the identification and treatment of atypical AFL (as defined in section 4.1.2), including role of HD wave relative to along-the-spline maps in identifying ablation target(s), and time of RF application to terminate atypical AFL

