5.3.3 Exclusion Criteria

1. Life expectancy less than 12 months

Clinical Investigation Plan

2. Women who are pregnant or nursing
3. Known intracardiac thrombus or myxoma verified within 48 hours of index ablation procedure
4. Myocardial infarction (MI) or unstable angina, or previous cardiac surgery within 60 days of index ablation procedure
5. Percutaneous coronary intervention (PCI) within 30 days of index ablation procedure
6. Documented cerebroembolic event within the past 12 months (365 days)
7. History of valve repair, presence of a prosthetic valve, or severe mitral regurgitation thought to require valve replacement or repair within 12 months
8. Awaiting cardiac transplantation or other cardiac surgery within the next 12 months (365 days)
9. Current acute illness or active systemic infection or sepsis
10. Currently enrolled in another clinical study that could confound the results of this study
11. Any cause for contraindication to ablation procedure or systemic anticoagulation
12. Presence of other anatomic or comorbid conditions, or other medical, social, or psychological conditions that, in the investigator's opinion, could limit the subject's ability to participate in the clinical study or to comply with follow-up requirements, or impact the scientific soundness of the clinical study results.
13. Vulnerable patient or individuals whose willingness to volunteer in a study, in the judgement of investigator or public authorities, could be unduly influenced by lack of or loss of autonomy
14. Indication-specific exclusion criteria including:
 - a. PersAF:
 - i. PersAF felt to be secondary to electrolyte imbalance, uncontrolled thyroid disease, or reversible or non-cardiac cause.
 - ii. LAD > 55 mm (parasternal long axis view)
 - iii. LVEF < 40%
 - iv. Uncontrolled heart failure or NYHA function class III or IV
 - v. Presence of implanted ICD/CRT-D.
 - b. VT:
 - i. VT/VF thought to be from channelopathies
 - ii. Active ischemia or other reversible cause of VT
 - iii. Incessant VT at time of procedure
 - iv. Implanted with a ventricular assist device (VAD) (e.g. TandemHeart)
 - v. Chronic NYHA Class IV heart failure
 - vi. Ejection fraction < 15%

Incessant VT is defined as continuous sustained VT that promptly recurs despite repeated intervention for termination over ≥ 3 hours.

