6.3 Pre-discharge Visit (In-hospital)

Prior to discharge after the study procedure, a Pre-discharge visit will be completed. The following information will be collected from each subject at the Discharge Visit:

- 12-lead ECG
- Collect ICD session records and interrogation reports if applicable
- Arrhythmia recurrence
 - For the purposes of this clinical study recurrence of arrhythmia is deemed to have occurred only when the arrhythmia is documented on ICD, ECG, or other monitoring device used per standard of care. Atrial arrhythmias 30 seconds or longer will be collected. Ventricular arrhythmias treated by an ICD, or lasting 30 seconds or longer will be collected
- Antiarrhythmic medications- any current class I/III AAD and dose
- Adverse events if applicable
- Protocol deviations if applicable

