6.5 Core Laboratory

A core lab will be used for the collection, interpretation, and collation of data collected from Holter monitoring.

Clinical Investigation Plan

The core lab will provide independent review of this data by appropriately trained personnel using standardized procedures to interpret Holter monitor tracings for adjudication of atrial arrhythmias. Findings will be communicated to the investigator and to Abbott. The core lab's adjudication findings will be used for analysis.

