8.7 Procedures for Accounting for Missing Data

Every effort will be made to collect all required data. All data available for the endpoints specified among the analysis population will be used. Missing data will not be imputed. Kaplan-Meier analysis will censor subjects withdrawn or otherwise lost-to-follow-up at last known visit.

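### Read literally, PersAF long-term success depends only on the month-12 48-hour Holter, so a documented relapse or re-ablation after day 90 can still count as success; report a labelled any-source rate beside it

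*Combined protocol and SAP*

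**What the plan says.** Section 4.1.1 gives two PersAF long-term success definitions. Both rest on "freedom from all atrial arrhythmias (AF/AFL/AT) greater than 30 seconds (as documented by 48-hr Holter at 12-month follow-up"). The first also requires no new or increased class I/III antiarrhythmic drug (AAD); the second disregards AAD use. Both sit under the line "Persistent AF (utilizing a 90-day blanking period following index ablation").

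On the source of evidence, Section 3.2 states "Evaluation of arrhythmia recurrence via Holter monitoring will be performed by an independent core laboratory", and Section 6.5, which covers Holter data only, says the core lab's "adjudication findings will be used for analysis". Repeat ablation appears separately in Section 4.1.3, as the "proportion of subjects without an additional ablation procedure to treat indicated cardiac arrhythmia".

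Other evidence is collected. Section 6.3 says "recurrence of arrhythmia is deemed to have occurred only when the arrhythmia is documented on ICD, ECG, or other monitoring device" used in routine care. Section 6.4.1 lists arrhythmia recurrence and other monitor documentation at both follow-up visits. Section 6.4.2 records ECGs, monitor records and repeat ablation at unscheduled visits. Section 7.3.1 says recurrence is reported within the descriptive endpoints, through the follow-up CRF. Section 8.2.2 plans Kaplan-Meier analysis in which blanked events are not failures, but names neither the time-to-event variable nor the event sources.

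On incomplete data, Sections 8.2.2 and 8.7 use what is available, and "Missing data will not be imputed".

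**The concern.** Long-term success is one of the two rates named in the first study objective, and a reader will take it as success of the index ablation. As worded, one 48-hour recording near month 12 decides the arrhythmia component. A patient who relapsed after blanking and was then re-ablated or cardioverted, or whose arrhythmia is intermittent, can have a clean recording and be counted as a success although the site holds proof of the recurrence. Reporting re-ablation as its own rate does not show how many re-ablated patients are among the successes.

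The readable text also leaves open how a PersAF patient without a month-12 Holter enters the rate. Two analysts could therefore obtain different long-term success rates from the same database.

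**Working it through.** The plan states no expected success rate or precision for this endpoint, so there is no figure to reproduce. The check sets the passages against each other and then sizes the gap under declared assumptions.

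**Blanking against the visit window.** Section 6.4.1 puts the 12-month visit at 360 ± 90 days, i.e. day 270 (360 − 90) to day 450 (360 + 90). Blanking ends on day 90, so the earliest scheduled month-12 Holter falls 270 − 90 = 180 days later. Blanking cannot affect that Holter. It can matter only for AAD changes or for other sources, including the unscheduled Holters that Table 2 (Section 6.4.5) allows.

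**Share of follow-up observed by the Holter** (2 days divided by visit day minus 90):

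- visit on day 270: 2/180 = 1.11%
- visit on day 360: 2/270 = 0.74%
- visit on day 450: 2/360 = 0.56%

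Continuous AF still present at month 12 would be seen. If episodes are brief and random (an assumption), 48 hours catches at least one with probability 1 − exp(−2 × daily rate): 6.4% at one episode per month, 12.5% at two per month, 24.9% at one per week.

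**Contrast within Section 4.1.1.** VT recurrence counts ICD therapy, follow-up recordings or intervention, with no single-test restriction. Only the PersAF definitions carry one.

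**Size of the gap, same patients, all with a month-12 Holter.** All inputs are assumed:

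- r = share with a documented recurrence or repeat ablation between day 91 and month 12
- q = share of those with a clean Holter
- a = share of those clean-Holter patients with an AAD started or increased

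On-or-off-AAD definition: gap = r × q, in percentage points.

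| r | q = 30% | q = 50% | q = 70% |
|---|---|---|---|
| 10% | 3 | 5 | 7 |
| 20% | 6 | 10 | 14 |
| 30% | 9 | 15 | 21 |

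Definition with the AAD component: gap = r × q × (1 − a). Over the same grid this gives 2.25 to 15.75 points at a = 25%, 1.5 to 10.5 at a = 50%, and 0.75 to 5.25 at a = 75%.

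**Denominator effect.** Take a hypothetical 300 PersAF patients. Of these, 200 have a Holter: 60 positive, and 10 of the 140 negatives have another documented recurrence. The other 100 have no Holter, and 10 of them have a documented recurrence. Exact (Clopper-Pearson) 95% intervals:

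| Rate | Count | Estimate (95% CI) |
|---|---|---|
| Holter-only | 140/200 | 70.0% (63.1–76.3) |
| Any-source, same 200 | 130/200 | 65.0% (58.0–71.6) |
| Any-source, the 90 recurrence-free without Holter excluded | 130/210 | 61.9% (55.0–68.5) |
| Any-source, those 90 as failures | 130/300 | 43.3% (37.6–49.1) |
| Any-source, those 90 as successes | 220/300 | 73.3% (67.9–78.3) |

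In the same patients the Holter-only rate can only equal or exceed the any-source rate. With different denominators the order can reverse (70.0% against 73.3%). The third row shows a trap: it keeps the recurrences found among patients without a Holter but drops their recurrence-free counterparts, which pulls the rate down.

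**The case against.** The strongest reply is that the sponsor probably means any recurrence after day 90 to count. Section 6.3 phrases its recurrence rule for the study as a whole, Section 6.4.1 lists recurrence separately from the Holter, Section 7.3.1 routes recurrence into the endpoints through a site form, and a single month-12 Holter cannot supply event times for a Kaplan-Meier curve. A reading that leaves blanking with almost nothing to do is the weaker one. Sections 3.2 and 6.5 say who reads Holters; they do not exclude other evidence. This stands as a reason to call the rule unresolved and not to assume that recurrences will be ignored. It does not remove the point, because no readable section ties those sources to the PersAF success rate.

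Redaction is a fair limit. Part of Section 8.1 and the later appendices are blacked out, and the table mockups are not visible, so a combining or denominator rule may exist there.

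A uniform, core-lab-read assessment is also a defensible choice. Any-source evidence varies with how intensively sites monitor: the 6-month visit may be by phone, follow-up ECGs are done only if applicable, and "Presence of implanted ICD/CRT-D" is a PersAF exclusion, so those devices will not supply recordings. That argues for keeping the Holter rate, not for reporting it alone.

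Finally, best- and worst-case bounds may seem to conflict with the no-imputation rule. They only display how much the unclassified patients could matter; no value is filled in for the reported estimate.

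**Conclusion.** The concern holds on the readable text, as a minor point. Followed literally, Section 4.1.1 lets patients with a documented post-blanking relapse or re-ablation count as long-term successes: under the on-or-off-AAD definition whenever the month-12 Holter is clean, and under the other definition unless an AAD was also started or increased.

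The size is unknown. The ranges above rest wholly on assumed r, q and a, and the gap is zero if no clean-Holter patient has other evidence of recurrence. The 300-patient counts are invented, including the one-third without a Holter; the readable text does not give the PersAF share of the 500 subjects. Sections 8.6 and 8.10 rule out hypothesis tests and pass/fail criteria, so what is affected is how the rate is read.

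**What to change.** In Sections 4.1.1 and 8.2.2, define two labelled PersAF 12-month success proportions, each with its denominator and an exact 95% interval:

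- **(a) Holter rate:** the core-lab month-12 Holter proportion as now worded.
- **(b) Any-source rate:** failure is AF/AFL/AT longer than 30 seconds after day 90 from any source already collected, or a repeat ablation for atrial arrhythmia after blanking. For the definition with the AAD component, a new or increased class I/III AAD after blanking is also a failure.

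Show (a) and (b) side by side in the common set of patients with a month-12 Holter. For (b) over all treated patients, label a recurrence-free patient without a month-12 Holter as unclassified, give the count, and show the two bounds (all failures, all successes). Do not drop these patients while keeping the recurrences among others without a Holter. If a Kaplan-Meier curve is shown for this endpoint, name the (b) events as its events. If a combining rule already exists in redacted text or the mockups, stating it in Section 4.1.1 settles which sources count.

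The cost is protocol and SAP wording plus a little programming; no new visit or test is needed. The drawback is that (b) may come out lower, depends on site monitoring, and mixes site-read with core-lab evidence, which is why (a) stays.

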4.1.2 Utility Objective

The second objective is to quantify and characterize the use of HD Grid and EnSite Precision with HD Wave in the electroanatomical mapping of PersAF or VT in real-world clinical settings.

Use of HD Grid and EnSite Precision with HD Wave will be quantified and characterized through the summary of the following:

- Overall procedure time: defined as time from initial catheter insertion to final catheter removal.
- Radiofrequency (RF) time: defined as duration of time RF energy is delivered
- Fluoroscopy time: defined as total time subject is exposed to fluoroscopy
- Mapping time associated with mapping arrhythmia: defined as the total cumulative mapping time and mapping time for the creation of each map (including any new or retrospective map created with Manual, AutoMap, and TurboMap mapping)
- Number of mapping points collected: defined as total number of mapping points collected for the creation of each map
- Number of mapping points used: defined as the total number of mapping points used in each map
- Number of used mapping points per minute: defined as the total number of mapping points used divided by the relative mapping time
- Substrate characteristics identified: for each type of arrhythmogenic substrate this will be defined as the frequency of substrate type identified in cases that attempted to identify the specific substrate

Clinical Investigation Plan

- Ablation strategy(s) used: defined by both the type of map used to define ablation strategy and the frequency each ablation strategy/target was used by physicians
- Role of HD Wave map relative to along-the-spline map in ablation strategy decision: as assessed by physician survey comparing maps generated with HD Wave electrode configuration to along-the-spline electrode configurations.
- Maneuverability of HD Grid catheter: defined as the ability to maneuver the HD Grid to each specified anatomic location if attempted, the ability to contact cardiac tissue, and the incidence of induced ectopic beats during maneuvering
- HD Grid electrogram quality relative to ablation catheter electrograms: defined as the proportion of electrograms collected with HD Grid that have better quality/less noise than electrograms collected with the ablation catheter at the same cardiac location as assessed by physician survey

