6.2 Procedure Visit

The procedure should be performed according to the IFU of the HD Grid mapping catheter, EnSite Precision™ Cardiac Mapping System, and any other medical devices used during the procedure. Physicians performing electroanatomical mapping and ablations must be qualified operators and trained on the study. Each physician who ablates during a particular case needs to be documented on the Procedure CRF.

The following information will be collected during the Procedure Visit:

- Antiarrhythmic medications- any current class I/III AAD and dose
- Anticoagulant medications
- Subject cardiac rhythm when they enter the EP lab
- Subject cardiac rhythm during mapping
- Mapping and ablation tools used during the procedure
- Procedural characteristics (set up and timing)
- Fluoroscopy time
- Mapping time (total time to collect mapping data and time for each map created/ retrospectively generated)
- Mapping points collected and used for each map created/ retrospectively generated
- Mapping location(s)
- Electrode configuration used for clinical electroanatomical mapping
- Map type(s) (i.e. Voltage, LAT, CFE, etc.)
- AutoMap settings used (if applicable)
- Arrhythmogenic substrate identified
- Field Scaling use
- Standard and HD Wave map comparisons
- Ablation strategy
- AutoMark settings used (if applicable)
- Cardioversions performed during procedure
- Attempt(s) at induction of arrhythmia as applicable before and after RF delivery
- Subject rhythm after completion of procedure

The entire case (procedure) must be recorded and stored on a study-specific USB (password-protected), provided by the Sponsor, and returned within a reasonable timeline to the Sponsor.

Protocol deviations (refer to Section 10.5 for details) that were observed during the procedure, which include any device used off-label during the procedure, will also be recorded at this time.

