6.2.2 Electroanatomical mapping

The HD Grid Mapping catheter must be used with EnSite Precision to generate a baseline electroanatomical map prior to ablation procedure. Complete contact with the cardiac wall should be achieved before collecting data. Mapping will be done per investigator discretion and is recommended to use an HD Wave electrode configuration for catheter set-up (see Appendix V). Additional maps may be created or retrospectively generated using TurboMap per physician standard practice for diagnostic purposes.

For comparison of HD wave and along-the-spline electrode configuration maps, any HD Wave configuration map used during the case should also be generated using the along-the-spline electrode configurations, preferably using TurboMap with the same geometry as baseline map (see Appendix V for details on configuration and transitions between map types). This may be done during the diagnostic procedure as part of standard of care procedure flow for relevant comparisons prior to ablation strategy determination. If not performed during the procedure, this should be performed after completion of the ablation procedure for comparison of maps resulting from different electrode configurations. Similarly, any along-the-spline electrode configuration map used during the procedure should have a comparable HD Wave configuration map generated for comparison.

For the purposes of this protocol, creating a map or mapping, is considered to be the process of collecting electroanatomical data points within heart via movement or positioning of the mapping catheter within the heart.

A retrospective map will be defined as the generation of a map that does not require collection of any new or additional electroanatomical data points but instead reuses already collected mapping data with new point collection or acquisition settings or electrode configurations selected (via TurboMap) or manual alteration of a copied open map.

Information related to each map generated, and comparison of any HD wave and respective along-the-spline maps will be reported on the appropriate CRF.

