6.2.3 Indication-specific Procedural Recommendations

6.2.3.1 Persistent AF:

Create a baseline geometry and map (at a minimum, collect baseline map, other maps may be collected or retrospectively generated per standard of care) of entire left atrium using HD Grid with HD Wave electrode configuration. Create or retrospectively generate any additional electroanatomical maps (may include generation of maps with along-the-spline configuration, preferably using TurboMap with same geometry; see Appendix V). Use the baseline HD Wave map and/or additional maps as clinically necessary, to identify ablation target(s), and use ablation catheter per IFU to perform ablation per standard of care. Assess acute procedural success. Collect additional maps and perform additional ablation as clinically necessary. Ablation to treat other arrhythmias that occur during the procedure are allowed per physician discretion and standard of care.

If the subject presents in atypical AFL at any time during the procedure or as a result of induction, diagnostic mapping and RF ablation will be allowed. If this occurs, HD Grid with HD Wave electrode configuration should be used to create diagnostic maps per standard of care. Create or retrospectively generate any additional electroanatomical maps (may include generation of maps with along-the-spline configuration, preferably using TurboMap with same geometry; see Appendix V). Use the HD Wave map and/or additional maps as clinically necessary, to identify ablation target(s), and use ablation catheter per

Clinical Investigation Plan

IFU to perform ablation per standard of care. Information related to diagnostic mapping and ablation of the atypical AFL will be collected.

6.2.3.2 VT:

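### Does counting retrospective TurboMap maps in mapping time leave mapping time and points per minute without a clear meaning?

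*Combined protocol and SAP*

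**What the plan says.** Section 4.1.2 (Utility Objective) defines mapping time in two parts: a cumulative total and a time for each map. A parenthesis sets the scope: "including any new or retrospective map created with Manual, AutoMap, and TurboMap mapping". Points collected and points used are also counted map by map. Used points per minute is "defined as the total number of mapping points used divided by the relative mapping time". No readable passage says more about that denominator.

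Section 6.2.2 (Electroanatomical mapping) fixes the terms. It says that "creating a map or mapping, is considered to be the process of collecting electroanatomical data points within heart via movement or positioning"; what is moved or positioned is the catheter. A retrospective map, by contrast, "does not require collection of any new or additional electroanatomical data points but instead reuses already collected mapping data", through TurboMap or by editing a copy of an open map. The two acts are worded as alternatives there ("Additional maps may be created or retrospectively generated using TurboMap per physician standard practice") and in section 6.2.3 ("Create or retrospectively generate any additional electroanatomical maps"). Section 6.2.2 also asks for paired maps: "any HD Wave configuration map used during the case should also be generated using the along-the-spline electrode configurations, preferably using TurboMap". An along-the-spline map used in the case should likewise have an HD Wave counterpart.

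Section 6.2 (Procedure Visit) lists the data item: "Mapping time (total time to collect mapping data and time for each map created/ retrospectively generated". Points collected and used are recorded for the same maps.

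Section 8.2.2 makes all endpoints descriptive, without hypothesis tests, and refers to table mockups for the layout of summaries. The mockups are not in the documents. The CRFs are held separately (Appendix II), and part of section 8.1 and Appendix V are redacted.

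**The concern.** If creating a map means collecting points with the catheter, a retrospective map has no creation time of its own. Section 4.1.2 nevertheless asks for one. It could be the software generation time, the acquisition time of the reused data, or their sum, and used points per minute inherits the same uncertainty.

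Retrospective maps should also be common. Section 6.2.2 asks for a paired map for each HD Wave or along-the-spline map used. It prefers TurboMap for the along-the-spline partner of an HD Wave map, and it lets the pairing wait until ablation is finished. If acquired maps and copies were averaged together, a reader could not tell whether a reported time per map described catheter work or regeneration. A fast copy could also inflate points per minute. Both quantities are named endpoints of the Utility Objective, so their meaning matters even without a test.

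**Working it through.** The plan states no figure for mapping time, points or share of retrospective maps, so there is nothing to reproduce. The check sets the sections side by side and then asks how much depends on assumptions from outside the documents.

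**1. Is the inclusion of retrospective maps a contradiction?** Section 4.1.2 includes them expressly, and the data item in section 6.2 matches it: both ask for a time for each retrospective map. The inclusion therefore looks deliberate. Section 6.2.2 defines words and does not forbid recording a generation time. The mismatch is one verb: section 4.1.2 says created where sections 6.2, 6.2.2 and 6.2.3 distinguish created from generated.

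**2. Is the total affected?** Section 6.2 describes the total as time spent collecting mapping data. That supports catheter time only, although section 4.1.2 does not repeat the limit.

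**3. Which rates are in doubt?** An acquired map has an acquisition time and no separate regeneration time, so the natural denominator is that map's own acquisition time. The doubt is confined to retrospective maps. An illustration, with every input assumed: a copy uses 2,000 points, its source data took 10 minutes to collect, and generation takes g = 1 or 5 minutes.

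| Denominator | g = 1 | g = 5 |
|---|---|---|
| Source acquisition time | 2,000/10 = 200 | 2,000/10 = 200 |
| Generation time | 2,000/1 = 2,000 | 2,000/5 = 400 |
| Sum of both | 2,000/11 = 182 | 2,000/15 = 133 |

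For one such map the highest reading is (10 + g)/g times the lowest: 11 at g = 1 and 3 at g = 5. An unlabelled rate for a retrospective map would thus be hard to read.

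**4. What would pooling do?** Let s be the share of maps that are retrospective, k the copy's recorded time over its source's acquisition time, and r the points used in the copy over those in the source. Assume that acquired maps are alike. Relative to acquired maps alone:

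- mean time per map = 1 − s(1 − k)
- mean points per minute = (1 − s) + s·r/k

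All inputs are assumed:

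| s | k | Time | Points/min, r = 1 | Points/min, r = 0.5 |
|---|---|---|---|---|
| 0.5 | 0.10 | 0.55 | 5.5 | 3.0 |
| 0.5 | 1/3 | 0.67 | 2.0 | 1.25 |
| 0.5 | 1 | 1.00 | 1.0 | 0.75 |
| 0.25 | 0.10 | 0.78 | 3.25 | 2.0 |
| 0.25 | 1/3 | 0.83 | 1.5 | 1.13 |
| 0.25 | 1 | 1.00 | 1.0 | 0.88 |

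For the first row: 1 − 0.5 × 0.9 = 0.55, and 0.5 + 0.5 × 1/0.10 = 5.5. The rate rises if r > k, falls if r < k, and does not move if r = k. The documents give none of s, k or r, so even the direction is open.

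**5. Does the plan call for pooling?** No. Section 4.1.2 defines time, points collected and points used for each map, and no passage asks for an average across map types. With the types in separate rows, s = 0 in the acquired row and both ratios equal 1 whatever k and r are. Such a report complies with the plan as written.

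**6. Can the types be separated at analysis?** Section 6.2 records time and points for each map, section 6.2.2 defines a retrospective map and sends information on each map to the CRF, and the whole case is recorded and returned to the sponsor. Section 8 allows further analysis of that recording. The listed map-type item (voltage, activation time and so on) is not itself an acquired-or-retrospective flag, so this step relies on the CRF or the recording.

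**The case for a change.** The strongest reply is that an endpoint definition should be readable without the mockups. Section 6.2 asks for a time for each retrospective map without saying what it measures. Reading the denominator in section 4.1.2 as the respective map's own time does not settle it, because for a retrospective map that time is the unspecified quantity. Paired maps are requested as routine, and section 4.1.3 carries the utility definitions over to atypical flutter. In a study whose purpose is to quantify use, the definition largely determines what a summary means.

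The textual part of this stands: the verb is loose and the denominator for retrospective maps is open. The harm does not follow, because it needs a pooled table that no passage requests.

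Two further links are weak. Section 8.8 speaks of acute endpoints on use of the catheter at 250 subjects without naming mapping time. Section 8.14 lists mapping time beside procedure, RF and fluoroscopy time, all case totals, so the total is the natural reading there, and section 6.2 describes that total as collection time.

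New wording would also gain little. A sentence defining the denominator for acquired maps would settle the case that is not in doubt. For retrospective maps someone must still choose a denominator or report no rate, and a table footnote does that as well as an amendment.

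**Conclusion.** No change to the plan is needed. One part is a clerical slip (created where generated was meant). The other is missing detail in a descriptive endpoint, which analysts would ordinarily fill by giving retrospective maps their own row and naming the time used.

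The size of any distortion cannot be derived from the documents. The factors above, from 0.55 to 1.00 for time and from 0.75 to 5.5 for points per minute, rest on assumed s, k and r and on assumed pooling. With the types kept apart, the acquired-map results are unaffected. No hypothesis test, success criterion, sample size or safety result uses these quantities.

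The conclusion assumes that the CRF or the case recording identifies which maps are retrospective, and that the mockups do not merge the two types without a label. Neither mockups nor CRFs are in the documents. A mockup that did merge them would need correcting at that level, and the endpoint as written would not stand in the way.
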